General	
The Principal Investigator was updated.
 
The radiolabeled dose was corrected to 32.8 μCi (1.21 MBq) throughout the protocol.
 
The discharge criteria were updated to remove plasma radioactivity levels below the limit of quantitation for 2 consecutive collections.
 
Editorial, formatting, and consistency updates throughout.
 
Amendments to abbreviations list to align with text.
 
Version 16 of the Investigator's Brochure was added to reference section.

Section 1.2 Summary of Nonclinical Pharmacokinetics	Updated in line with Version 16 of the Investigator's Brochure.
Section 1.3 Summary of Clinical Experience	Updated in line with Version 16 of the Investigator's Brochure.
Section 3.3 Selection of Doses in the Study	Updated to correct committed effective radiation dose of 0.997 mSv.
Appendix 4: Contraception Guidance	
Updated to allow for the reduction in duration of contraception from 120 days to 90 days based on new available data within Version 16 of the Investigator's Brochure.
 
Clarification was included to highlight vasectomy applied to male subjects.

SYNOPSIS

Study Title

A Phase 1, open-label, nonrandomized study to investigate the mass balance recovery and metabolic profile of ^{14}C -bemcentinib following single oral administration in healthy male subjects.

Objectives and Endpoints

Objectives	Endpoints
Primary: 
to determine the mass balance recovery (urine and feces) and route and rate of elimination of ^{14}C-bemcentinibto determine the PK of total radioactivity in plasma and whole blood and of bemcentinib in plasma after a single oral dose of ^{14}C-bemcentinib in healthy male subjects.	
total radioactivity recovery ($\text{fe}_{\text{t1-t2}}$) in urine and fecesPK parameters including, but not limited to, $\text{AUC}_{0-\infty}$, $\text{AUC}_{0-\text{tlast}}$, C_{max}, t_{max}, and $\text{t}_{1/2}$ for bemcentinib in plasma and total radioactivity in plasma and whole blood and urinary recovery of bemcentinib ($\text{fe}_{\text{t1-t2}}$).
Secondary: 
to determine the metabolite profile of ^{14}C-bemcentinib in plasma, urine, and fecesto identify the chemical structure of the major* metabolites of bemcentinib *based on the MIST guidelines: >10% of bemcentinib parent exposure in plasma after oral administrationto assess safety and tolerability of ^{14}C-bemcentinib when administered to healthy subjects.	
quantitative metabolic profiles of bemcentinib in plasma and excretaidentification of bemcentinib major metabolites in plasma (>10% relative total drug related exposure) and excreta (>10% of excreted dose)incidence and severity of AEsincidence of laboratory abnormalities, based on hematology, clinical chemistry, and urinalysis test results12-lead ECG parametersvital signs measurementsphysical examinations.

Abbreviations: AE = adverse event; $\text{AUC}_{0-\infty}$ = area under the concentration-time curve from time 0 extrapolated to infinity; $\text{AUC}_{0-\text{tlast}}$ = area under the concentration-time curve from time 0 to the time of the last quantifiable concentration; C_{max} = maximum observed concentration; ECG = electrocardiogram; $\text{fe}_{\text{t1-t2}}$ = percentage of the dose administered recovered over the time interval t1 to t2; MIST = Metabolites in Safety Testing; PK = pharmacokinetics; $\text{t}_{1/2}$ = apparent terminal elimination half-life; t_{max} = time of the maximum observed concentration.

Study Design

This will be a Phase 1, open-label, nonrandomized, single oral dose study in healthy male subjects.

Potential subjects will be screened to assess their eligibility to enter the study within 28 days prior to dose administration. Subjects will be admitted into the study site on Day -1 and be confined to the study site until at least Day 8. On Day 1, subjects will receive a single oral dose of ^{14}C -bemcentinib. Subjects will be discharged if the following discharge criteria are

met: $\geq 90\%$ mass balance recovery and $< 1\%$ of the total radioactive dose is recovered in combined excreta (urine and feces) in 2 consecutive 24-hour periods.

If these discharge criteria are not met by Day 8, subjects will be required to remain resident until discharge criteria are met, up to Day 15. If criteria are not met by Day 15, subjects may be asked to collect 24-hour excreta samples on up to 2 further occasions on a nonresidential basis to allow extrapolation of urinary and fecal excretion. If needed, the 2 additional 24-hour nonresidential collections will start on the morning of Days 22 and 29 (to be brought into the study site at the end of the collection interval on Days 23 and 30, respectively). If on the second occasion the subject has still not met the desired criterion, then the subject will be discharged from the study, per investigator and sponsor decision.

Number of Subjects

Up to 8 subjects will be enrolled and studied as a single group in order that 6 subjects complete the study.

Diagnosis and Main Criteria for Inclusion

Healthy male subjects aged between 35 and 55 years (inclusive) with a body mass index between 18.0 and 32.0 kg/m² (inclusive).

Investigational Medicinal Products, Dose, and Mode of Administration

Each subject will receive a single oral dose of █ mg of ¹⁴C-bemcentinib as two █-mg capsules containing approximately █ μ Ci (█ MBq) on the morning of Day 1, 30 minutes after starting a standard high-fat breakfast.

Duration of Subject Participation in the Study

Planned screening duration: approximately 4 weeks.

Planned study duration (screening to outpatient visit [if required]): a maximum of approximately 9 weeks.

Statistical Methods

Pharmacokinetic parameters will be derived by standard noncompartmental analysis.

Pharmacokinetic and safety parameters will be listed and summarized. No formal statistical analysis will be performed.

TABLE OF CONTENTS

TITLE PAGE	1
SPONSOR APPROVAL.....	2
INVESTIGATOR AGREEMENT	3
STUDY IDENTIFICATION.....	4
PROTOCOL AMENDMENT SUMMARY OF CHANGES	5
SYNOPSIS	6
TABLE OF CONTENTS	8
LIST OF TABLES	10
LIST OF ABBREVIATIONS	11
1. INTRODUCTION.....	12
1.1. Overview	12
1.2. Summary of Nonclinical Pharmacokinetics	12
1.3. Summary of Clinical Experience	14
1.4. Study Rationale	15
1.5. Benefit-risk Assessment.....	15
2. OBJECTIVES AND ENDPOINTS.....	15
3. INVESTIGATIONAL PLAN	16
3.1. Overall Study Design and Plan	16
3.2. Discussion of Study Design	17
3.3. Selection of Doses in the Study	18
4. SELECTION OF STUDY POPULATION.....	18
4.1. Inclusion Criteria.....	18
4.2. Exclusion Criteria.....	19
4.3. Subject Number and Identification.....	20

ICF	informed consent form
ICH	International Council for Harmonisation
ICRP	International Commission on Radiological Protection
IFN	interferon
IMP	investigational medicinal product
P-gp	P-glycoprotein
PK	pharmacokinetic
SAE	serious adverse event
t _½	apparent plasma terminal elimination half-life
t _{max}	time of the maximum observed plasma concentration

1. INTRODUCTION

Refer to the investigator's brochure (IB)¹ for detailed information concerning the available pharmacology, toxicology, drug metabolism, clinical studies, and adverse event (AE) profile of the investigational medicinal product (IMP).

1.1. Overview

Bemcentinib, formerly known as BGB324 and R428, is being developed for the treatment of a range of solid tumors and myeloid malignancies, as well as SARS-CoV-2 infection (COVID-19). BerGenBio ASA (BerGenBio)-sponsored and investigator-led studies are ongoing in patients with non-small cell lung cancer, metastatic melanoma, acute myeloid leukemia (AML), myelodysplastic syndrome, metastatic pancreatic cancer, glioblastoma, malignant mesothelioma, and COVID-19. Bemcentinib is being administered in various studies as monotherapy and in combination with erlotinib, cytarabine, decitabine, pembrolizumab, docetaxel, cisplatin, nab-paclitaxel, gemcitabine, and dabrafenib/trametinib.

In previous and ongoing studies bemcentinib is taken orally, initiated at a dose of 400 mg once daily for a 3-day loading period, followed by a maintenance dose of 200 mg daily.

Bemcentinib is a small molecule AXL kinase inhibitor which has demonstrated potent and selective inhibition of AXL in biochemical and cell-based kinase inhibition assays. In the oncology setting bemcentinib has been shown in vitro to inhibit cell proliferation in a number of different cell lines and induce apoptosis and cell death in acute myeloid leukemia cell lines. Bemcentinib showed pharmacological efficacy as a single agent and in combination with targeted chemo- or immune-checkpoint inhibitors in vivo in a variety of hematologic and primary and metastatic solid tumor models. As a single agent, bemcentinib inhibited tumor growth and prolonged survival in human acute myeloid leukemia xenograft models and syngeneic bone marrow transplantation mouse models and affected the expansion and survival of myelodysplastic cells. AXL is a recognized therapeutic target for the treatment of cancer and is an important negative regulator of type I interferon (IFN) responses that are important for both anti-cancer treatments and cellular anti-viral responses.

The AXL pathway is a mechanism utilized by several enveloped viruses to enter host cells and dampen viral immune response. The AXL receptor mediates entry of enveloped viruses such as Zika and Ebola through "apoptotic mimicry". Phosphatidylserine on the viral envelope is tethered to AXL by its bound ligand, growth arrest-specific 6, leading to virus internalization. Viruses also activate AXL signal transduction that dampens key anti-viral type I IFN responses. Preclinical data show that AXL-mediated internalization and Type 1 IFN suppression extend to SARS-CoV-2 and that bemcentinib acts on 2 host pathways to inhibit coronavirus replication, namely prevention of viral entry and enhanced anti-viral IFN response.

1.2. Summary of Nonclinical Pharmacokinetics

Nonclinical repeat dose toxicity studies were performed using daily oral gavage doses of bemcentinib administered to mice, rats, dogs, and monkeys. For oral administration, bemcentinib was prepared as a suspension in 0.5% (weight/volume [w/v]) hydroxypropyl

methyl cellulose in 0.15% (w/v) polysorbate 80, unless otherwise stated. Bemcentinib was not well tolerated in dogs due to significant gastrointestinal toxicity. Based upon the high plasma exposure and reasonable tolerability to bemcentinib in range-finding studies, mice and monkeys were selected for repeat dose Good Laboratory Practice (GLP) toxicity studies.

Single doses of bemcentinib were administered to male and female Sprague Dawley rats to identify the maximum tolerated dose. Bemcentinib was administered by oral gavage at doses of 100, 200, 600, and 1000 mg/kg (equivalent to 600, 1200, 3600, and 6000 mg/m²) to 3 rats/sex/group. All animals survived until scheduled euthanasia. Minimal bemcentinib-related changes were identified, with no bemcentinib-related effects identified as gross findings.

Repeat dose studies with bemcentinib were conducted in mice, rats, dogs, and monkeys. Bemcentinib was administered orally once daily for 10 days (rats and dogs) in non-GLP studies and for 28 days in GLP studies in mice and monkeys. Once and twice daily dosing for a total of 9 days was also investigated in a non-GLP monkey study. In the 28-day GLP studies, the treatment period was followed by a treatment-free recovery period of 14 or 16 days, in monkeys and mice respectively, in order to assess the reversibility of any treatment-related effects and for evidence of delayed toxicity. Initial toxicology work was conducted in line with International Council for Harmonisation S9 guidelines to support the initial oncology. Additionally, a 26-week GLP study was also conducted in the mouse along with a 39-week GLP study conducted in monkeys.

Pharmacokinetic (PK) studies were conducted both in vitro and in vivo, to elucidate the PK profile of bemcentinib and support clinical pharmacology investigations. Bemcentinib has good in vitro permeability and is a poor substrate for P-glycoprotein (P-gp), suggesting good systemic availability after oral dosing. Animal studies in which bemcentinib was dosed orally and intravenously showed high bioavailability indicating that bemcentinib is extensively absorbed from the gastrointestinal tract.

Protein binding of bemcentinib in human plasma was approximately 90% and 91.8% in mice, which was similar to that observed in rats, dogs and monkeys. The volume of distribution at steady state for bemcentinib was large (30-32 L/kg) and consistent across species, while clearance was moderate to high (19 - 43 mL/min/kg) with some variability. The time of the maximum observed plasma concentration (t_{max}) occurred late in the rat (8.9-13.3 hours), dog (14.0-18.0 hours), and monkey (6.7-28 hours). Data generated during a mouse absorption, distribution, metabolism, and excretion study indicate that bemcentinib is extensively distributed into tissue and that tissue concentrations were higher in comparison to plasma with a half-life of elimination between 11 and 14 hours.

Incubation of bemcentinib with human liver cells demonstrate that bemcentinib is a low-turnover compound in hepatocytes (half-life [t_{1/2}] >240 mins) and that in liver microsomes cytochrome P450 (CYP)3A4 and flavin containing dimethylaniline monooxygenase 1 are responsible for metabolism. Bemcentinib was found to inhibit CYP3A4 and CYP2D6 and to induce CYP3A4 and there is a moderate risk of interactions with co-administered drugs that are CYP3A4 or CYP2D6 substrates. Bemcentinib was found to weakly inhibit OATP1B1 and OCT1 and moderately inhibit P-gp and breast cancer resistance protein.

Bemcentinib was found to be an in vitro substrate of breast cancer resistance protein and MDR1 ABC (efflux) transporters under monolayer assay conditions.

1.3. Summary of Clinical Experience

To date, 1 Phase I study (BGBC001) has been completed in healthy volunteers and another Phase I food and gastric effect study (BGBC018) has completed recruitment and is in the final stages of reporting. Two Phase Ib/II company-sponsored clinical studies (BGBC003 and BGBC008) are currently ongoing in patients with advanced cancers. Another Phase Ib/II company-sponsored clinical study in non-small cell lung cancer (BGBC004) has completed patient recruitment and the clinical study report (CSR) is currently being finalized. One Phase II study (BGBC007) evaluating bemcentinib in combination with pembrolizumab in patients with triple negative breast cancer was terminated due to pre-defined futility.

There was also 1 company-sponsored study (BGBC020) and 1 investigator-led study (BGBIL019) evaluating bemcentinib plus standard of care in patients hospitalized with COVID-19 that have completed patient recruitment. Both studies have had last patient last visit and the final CSRs are being developed. In addition, 3 investigator-led studies in the oncology setting are ongoing, and 3 have completed patient enrollment.

Clinical study BGBC001, a Phase 1 first-in-human study that investigated the safety and PK of bemcentinib, has completed. Single ascending oral doses of bemcentinib in the range of 50 to 1500 mg were administered under fasted conditions to 32 healthy male subjects aged 18 to 45 years. Seven of these subjects were also administered bemcentinib at the same dose under fed conditions.

Bemcentinib was shown to have a predictable PK profile and long plasma half-life, allowing for different dosing options. Modelling of the PK data from this study has indicated that the most effective approach to rapidly achieving steady state is to administer a series of loading doses followed by a lower daily maintenance dose.

The administration of a single oral dose of bemcentinib was well tolerated up to 1000 mg. A single oral dose of 1500 mg was not well tolerated as demonstrated by the review of AEs. There were no serious adverse events (SAEs) reported in this study and all AEs resolved spontaneously. There were no clinically significant changes from screening in laboratory safety parameters, no clinically significant changes in vital signs, and no clinically significant abnormalities in electrocardiogram (ECG) parameters during the study. The most commonly occurring AEs were gastrointestinal disorders, particularly diarrhea and nausea.

In clinical study BGBC001, systemic exposure to bemcentinib increased approximately dose proportionately. The geometric mean $t_{1/2}$ was 45.6 to 88.7 hours. Between-subject variability in systemic exposure (area under the plasma concentration-time curve [AUC] from time 0 extrapolated to infinity [$AUC_{0-\infty}$] and maximum observed plasma concentration [C_{max}]) to bemcentinib at 100 to 1500 mg (PK parameters were only available in 2 subjects at 50 mg) was generally high (geometric coefficient of variation of 25.8% to 96.7% for $AUC_{0-\infty}$ and C_{max} , respectively), most probably reflecting a variable extent of absorption. The median t_{max} was 8 to 23 hours for doses ranging from 50 to 1500 mg, reflecting a slow absorption process. The geometric mean value for C_{max} after 200 and 400 mg single doses were 36.8 and

69.1 ng/mL, respectively. The geometric mean value for $AUC_{0-\infty}$ after 200 and 400 mg single doses were 3240 and 6290 h*ng/mL, respectively.

Following administration of bemcentinib with food to subjects who had previously received bemcentinib, there was an increase in systemic exposure in 3 subjects (50% or more), no appreciable change in 3 subjects, and an apparent reduction in systemic exposure (40%) in 1 subject. While C_{max} and AUC from time 0 to 48 hours under fed conditions were 29% and 21% greater, respectively, compared to fasted conditions, the 95% confidence intervals of the ratio (fed/fasted) included 100%, indicating lack of statistically significant effect of food on bemcentinib with Formulation 1. In a separate healthy volunteer food effect study (BGBC018) where 24 subjects received a single dose of 400 mg bemcentinib, the C_{max} and AUC from time 0 to the time of the last quantifiable concentration ($AUC_{0-tlast}$) were increased by 60% and 70%, respectively, under fed conditions compared to fasted conditions. There was also a 60% reduction in the coefficient of variation in the fed state compared to fasted.

1.4. Study Rationale

The purpose of this study is to determine mass balance recovery and identification of potential metabolites of bemcentinib which will enable the planning and design of future studies. The previously established ^{14}C labeling site of the active moiety of bemcentinib, which was used in the preclinical package for the radioburden calculation, is believed to provide the potential to monitor all of the unknown metabolites representing >10% of the parent compound as well as to determine the mass balance recovery (urine and feces).

1.5. Benefit-risk Assessment

Healthy subjects in the current study will not receive any health benefit (beyond that of an assessment of their medical status) from participating in the study. The risks of participation are primarily those associated with adverse reactions to the study treatments, although there may also be some discomfort from collection of blood samples and other study procedures. The radioactive dose is an acceptable dose to give to healthy male subjects. More information about the known and expected benefits, risks, and reasonably anticipated AEs associated with bemcentinib may be found in the IB.¹

2. OBJECTIVES AND ENDPOINTS

Table 1 shows the objectives and endpoints of the study.

Table 1: Objectives and Endpoints

Objectives	Endpoints
Primary: 
to determine the mass balance recovery (urine and feces) and route and rate of elimination of ¹⁴C-bemcentinibto determine the PK of total radioactivity in plasma and whole blood and of bemcentinib in plasma after a single oral dose of ¹⁴C-bemcentinib in healthy male subjects.	
total radioactivity recovery (fe_{t1-t2}) in urine and fecesPK parameters including, but not limited to, AUC_{0-∞}, AUC_{0-tlast}, C_{max}, t_{max}, and t_{1/2} for bemcentinib in plasma and total radioactivity in plasma and whole blood and urinary recovery of bemcentinib (fe_{t1-t2}).
Secondary: 
to determine the metabolite profile of ¹⁴C-bemcentinib in plasma, urine, and fecesto identify the chemical structure of the major* metabolites of bemcentinib *based on the MIST guidelines: >10% of bemcentinib parent exposure in plasma after oral administrationto assess safety and tolerability of ¹⁴C-bemcentinib when administered to healthy subjects.	
quantitative metabolic profiles of bemcentinib in plasma and excretaidentification of bemcentinib major metabolites in plasma (>10% relative total drug related exposure) and excreta (>10% of excreted dose)incidence and severity of AEsincidence of laboratory abnormalities, based on hematology, clinical chemistry, and urinalysis test results12-lead ECG parametersvital signs measurementsphysical examinations.

Abbreviations: AE = adverse event; AUC_{0-∞} = area under the concentration-time curve from time 0 extrapolated to infinity; AUC_{0-tlast} = area under the concentration-time curve from time 0 to the time of the last quantifiable concentration; C_{max} = maximum observed concentration; ECG = electrocardiogram; fe_{t1-t2} = percentage of the dose administered recovered over the time interval t₁ to t₂; MIST = Metabolites in Safety Testing; PK = pharmacokinetics; t_{1/2} = apparent terminal elimination half-life; t_{max} = time of the maximum observed concentration.

3. INVESTIGATIONAL PLAN

3.1. Overall Study Design and Plan

This will be a Phase 1, open-label, nonrandomized, single oral dose study in healthy male subjects.

Potential subjects will be screened to assess their eligibility to enter the study within 28 days prior to dose administration. Up to 8 subjects will be enrolled to ensure that 6 subjects complete the study. Subjects will be admitted into the study site on Day -1. On the morning of Day 1, all subjects will receive a single oral dose of [REDACTED] mg containing approximately [REDACTED] μCi ([REDACTED] MBq) of ¹⁴C-bemcentinib, 30 minutes after starting a standard high-fat breakfast.

Subjects will be confined to the study site until at least Day 8. Subjects will be discharged from the study site on Day 8 if the following discharge criteria are met:

- $\geq 90\%$ mass balance recovery, and
- $<1\%$ of the total radioactive dose is recovered in combined excreta (urine and feces) in 2 consecutive 24-hour periods.

If these discharge criteria are not met by Day 8, subjects will be required to remain resident until discharge criteria are met, up to Day 15. If criteria are not met by Day 15, subjects may be asked to collect 24-hour excreta samples on up to 2 further occasions on a nonresidential basis to allow extrapolation of urinary and fecal excretion. If needed, the 2 additional 24-hour nonresidential collections will start on the morning of Days 22 and 29 (to be brought into the study site at the end of the collection interval on Days 23 and 30, respectively). If on the second occasion the subject has still not met the desired criterion, then the subject will be discharged from the study, per investigator and sponsor decision.

Subjects experiencing emesis during the first 4 hours postdose may be discharged on the same day from the study site, provided there are no safety concerns, and after discharge study procedures are performed.

The total duration of study participation for each subject (from screening to outpatient visit [if required]) is anticipated to be a maximum of approximately 58 days.

The start of the study is defined as the date the first subject signs an informed consent form (ICF). The point of enrollment occurs at the time of subject number allocation. The end of the study is defined as the date of the last subject's last assessment (scheduled or unscheduled).

A Schedule of Assessments is presented in [Appendix 6](#).

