8.3. Pharmacokinetic Analyses

Pharmacokinetic parameters of bemcentinib in plasma and urine, and total radioactivity in plasma and whole blood will be determined using standard noncompartmental methods, where data allow. Full details of PK parameters will be presented in the statistical analysis plan for this study.

Pharmacokinetic parameters will be listed and summarized. No formal statistical analysis will be performed.

The mass balance recovery of total radioactivity (percentage of the dose administered recovered in urine, feces, and total excreta) will be calculated by the radioanalysis laboratory.

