Appendix 6: Schedule of Assessments

Study Procedures	Screening	Day - 1	Days 1 to 8 ^a	Discharge ^b Days 8 to 15	Outpatient Visit Days 22 to 29
Informed consent	X				
Inclusion/exclusion criteria	X	X			
Demographic data	X				
Medical history	X	X ^c			
Urinary drug screen	X	X			
Alcohol breath test	X	X			
Cotinine test	X	X			
Serology	X				
Height and body weight	X				
Blood sampling for pharmacogenetic profiling ^d			Day 1 (predose)		
Study residency:					
Check-in		X			
Check-out				X	
Nonresidential visit	X				X
Study treatment administration:					
¹⁴ C-bemcentinib			Day 1 oral administration (0 hours) (30 minutes after starting a high-fat breakfast)		
Pharmacokinetics:					
Blood sampling for bemcentinib concentration (plasma)			Predose, 15 and 30 minutes, 1, 1.5, 2, 2.5, 3, 4, 6, 8, 12, 16, 24, 36, 48, 72, 96, 120, 144, and 168 hours following the oral dose	192, 216, 240, 264, 288, 312, and 336 hours postdose	
Blood sampling for total radioactivity (whole blood and plasma)			Predose, 15 and 30 minutes, 1, 1.5, 2, 2.5, 3, 4, 6, 8, 12, 16, 24, 36, 48, 72, 96, 120, 144, and 168 hours following the oral dose	192, 216, 240, 264, 288, 312, and 336 hours postdose ^a	

Study Procedures	Screening	Day - 1	Days 1 to 8 ^a	Discharge ^b Days 8 to 15	Outpatient Visit Days 22 to 29
Blood sampling for metabolite profiling and identification (plasma ^g)			Predose, 15 and 30 minutes, 1, 1.5, 2, 2.5, 3, 4, 6, 8, 12, 16, 24, 36, 48, 60, 72, 96, 120, 144, and 168 hours following the oral dose		
Urine collection for bemcentinib ^j concentration, total radioactivity, and metabolite profiling ^g and identification			Predose (-3 to 0 hours) ^h , 0 to 12, 12 to 24, 24 to 48, 48 to 72, 72 to 96, 96 to 120, 120 to 144, 144 to 168 hours postdose ⁱ	168 to 192, 192 to 216, 216 to 240, 240 to 264, 264 to 288, 288 to 312, and 312 to 336 hours postdose ^a	Days 22 to Day 23, Days 29 to Day 30 ^e
Fecal collection for total radioactivity and metabolite profiling ^g and identification			Predose (from check-in to 0 hours) ^h , 0 to 12, 12 to 24, 24 to 48, 48 to 72, 72 to 96, 96 to 120, 120 to 144, 144 to 168 hours postdose ⁱ	168 to 192, 192 to 216, 216 to 240, 240 to 264, 264 to 288, 288 to 312, and 312 to 336 hours postdose ^a	Days 22 to Day 23, Days 29 to Day 30 ^e
Safety and tolerability:					
Adverse event recording	X	X	Ongoing	X	X
Prior/concomitant medication monitoring	X	X	Ongoing	X	X
Clinical chemistry, hematology, and urinalysis	X	X		X	

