Blood pressure and pulse rate ^f	X	X	Predose and 2, 4, 8, 24, and 48 hours postdose	X	
Oral body temperature	X	X		X	
12-lead electrocardiogram	X	X	Predose and 2 and 24 hours postdose	X	
Physical examination		X		X ^k	

^a Additional 24-hour collections (urine and feces) for radioanalysis may continue up to Day 15 if mass balance recovery is not adequate or radioactivity is still being eliminated in excreta. Subjects will be discharged when the following criteria are met: ≥90% mass balance recovery and <1% of the total radioactive dose is recovered in excreta (urine and feces) in 2 consecutive 24-hour periods. If this is the case, subjects will be asked to remain resident within the clinical research unit for a further period (up until Day 15).

^b Discharge will be from Day 8 to Day 15 depending on radioactivity elimination.

^c Interim medical history.

^d On Day 1, a blood sample will be collected and stored for subsequent assessment of the pharmacogenetic profile of bemcentinib in order to explore the influence of pharmacogenetic factors on the pharmacokinetics and safety.

^e If discharge criteria (mass balance recovery) is not adequate ($\leq 90\%$ mass balance recovery, and $>1\%$ of the total radioactive dose is recovered in excreta [urine and feces] in 2 consecutive 24-hour periods) are not met by Day 8, subjects will be required to remain resident until discharge criteria are met, up to Day 15. If criteria are not met by Day 15, subjects may be asked to collect 24-hour excreta samples on up to 2 further occasions on a nonresidential basis to allow extrapolation of urinary and fecal excretion. If needed, the 2 additional 24-hour nonresidential collections will start on the morning of Days 22 and 29 (to be brought into the study site at the end of the collection interval on Days 23 and 30, respectively). If on the second occasion the subject has still not met the desired criterion, then the subject will be discharged from the study, per investigator and sponsor decision.

^f Blood pressure and pulse rate will be measured singly followed by at least 5 minutes in the supine position.

^g Plasma samples for metabolite profiling will be selected after confirming the total radioactivity time profile. Urine and fecal samples for metabolite profiling will be selected after confirming total radioactivity time profile in excreta.

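### Does the lack of an extrapolation rule for the Day 22 and Day 29 collections undermine the primary mass balance recovery?

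*Combined protocol and SAP*

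**What the plan says.** Section 3.1, the synopsis and Appendix 6 footnote e describe the same sequence. Residence and continuous collection last until the discharge criteria are met, at the latest Day 15. After that come optional "24-hour excreta samples on up to 2 further occasions on a nonresidential basis to allow extrapolation of urinary and fecal excretion". The schedule places them at "Days 22 to Day 23, Days 29 to Day 30". Section 3.1 closes the sequence: "If on the second occasion the subject has still not met the desired criterion, then the subject will be discharged from the study".

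The first primary endpoint is total radioactivity recovery in urine and feces. The notes to Table 1 define fe as the "percentage of the dose administered recovered over the time interval" t1 to t2. Section 8.3 says the radioanalysis laboratory will calculate mass balance recovery as the "percentage of the dose administered recovered in urine, feces, and total excreta". The same section adds: "Full details of PK parameters will be presented in the statistical analysis plan for this study". The text of that plan is not in the combined document reviewed here. Section 8.3 mentions no interpolation or extrapolation and does not comment on uncollected intervals.

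**The concern.** The late samples have a stated purpose that the analysis section never takes up. Read literally, recovered dose is a sum of measured amounts, and such a sum gives nothing for days on which nothing was collected. A subject who goes through the whole fallback has 13 uncollected days between Day 15 and Day 30. For that subject a reader could not tell dose that was excreted but not collected from dose retained in the body. Recovery is the first primary endpoint and only 6 completers are planned, so one or two such subjects could move the reported mean.

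Two wording points lie nearby. The second discharge criterion needs less than 1% "of the total radioactive dose is recovered in excreta (urine and feces) in 2 consecutive 24-hour periods", which isolated single-day collections cannot show. Appendix 6 footnote i also counts three recovery criteria where two are listed.

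**Working it through.** **Calendar.** With 0 h on the morning of Day 1, Day d starts at 24 × (d − 1) h. Day 8 is 168 h and Day 15 is 336 h, as in Appendix 6. Screening of 28 days plus Day 30 gives 58 days, the maximum participation stated in Section 3.1. Days 22-23 are 504-528 h and Days 29-30 are 672-696 h.

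- Gap 1: 504 − 336 = 168 h = 7 days.
- Gap 2: 672 − 528 = 144 h = 6 days.
- Total: 312 h = 13 days, or 7 days if only the Day 22 sample is taken.

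**Size of the gap.** The document gives no half-life for total radioactivity and no absorbed fraction for this study. Assume that absorbed radioactivity leaves first-order at the parent plasma half-life h (45.6 to 88.7 h, Section 1.3) and that unabsorbed dose passes early. Let S(t) = 2^(−t/h), A = fraction absorbed and R = eventual recovery.

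- Omitted = R × A × [S(336) − S(504) + S(528) − S(672)]
- Collected late = R × A × [S(504) − S(528) + S(672) − S(696)]

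At h = 88.7, S at 336, 504, 528, 672 and 696 h is 0.0724, 0.0195, 0.0162, 0.0052 and 0.0043. The brackets are about 0.0638 and 0.0042.

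| h (h) | A | R | Omitted (points) | Collected late (points) |
|---|---|---|---|---|
| 88.7 | 1 | 1 | 6.38 | 0.42 |
| 88.7 | 0.75 | 0.95 | 4.55 | 0.30 |
| 63.7 | 1 | 1 | 2.42 | 0.11 |
| 45.6 | 1 | 0.88 | 0.52 | 0.01 |
| 45.6 | 0.5 | 0.88 | 0.26 | 0.01 |

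At h = 63.7 with A = R = 1, output over 288-312 h is exactly 1% of dose. That is where this smooth model first leads to the fallback through the rate criterion. The 45.6 h rows reach it only because R is below 90%.

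**One subject in full (88.7 h, A = 0.75, R = 0.95).**

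- Recovered by 336 h: 95 × (1 − 0.75 × 0.0724) = 89.8%.
- Sum of all collected samples: 89.8 + 0.3 = 90.1%.
- Excreted by Day 30: 95 × (1 − 0.75 × 0.0043) = 94.7%.

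**A second route.** Start from an assumed 1% of dose in the last resident 24 h and let r = 2^(−24/h). The omitted amount is the sum of r^j over j = 1 to 7 and j = 9 to 14. This gives 2.2 points at 45.6 h, 4.3 at 88.7 h and 7.0 at an assumed 177.4 h. A flat profile gives the upper bound of 13.

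**What the definition implies.** fe is defined over an interval. For a subject resident to Day 15, fe over 0-336 h comes from continuous collection and has no gap. An uncollected interval has no fe value, which is not the same as a value of zero. The shortfall therefore concerns a different quantity: dose excreted by Day 30.

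**The case for a change.** The strongest case for a change is that a primary endpoint should not leave a method to be chosen after the data are seen. The method matters. With 1% of dose in the last resident day and h = 88.7, linear interpolation fills 5.1 points and log-linear 4.3. The deferral to the SAP names PK parameters, while mass balance goes separately to the laboratory, so the SAP may not settle it. The fallback may also be common. With 50% absorbed at 88.7 h the smooth model avoids it at 95-100% eventual recovery, but a model with discrete stools sends roughly 59-72% of such subjects there. In a stool simulation of 3000 subjects per case, a log-linear fill was nearer the truth than zero in 93-99% of subjects.

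Much of this stands: Section 8.3 is silent, the calendar is right, and a bare sum would be a poor description of Day 30 excretion. It still does not change the primary value, because observed recovery would remain primary under any sensible rule. The choice of method is worth 5.1 − 4.3 = 0.8 points in one subject, or 0.8 / 6 = 0.13 points in a mean of six. A detailed rule would not be precise either. At 88.7 h the simulated error of the fill ran from −5.2 to +6.4 points (5th to 95th percentile) with a stool on 80% of days, and from −3.6 to +3.3 with a stool on 95%. That is of the same order as the omission. The anchoring and interpolation details are matters of judgement, best made with the excretion profile in hand.

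The wording points carry no weight. Discharge follows the second late collection whether or not the criterion is met. The count of three in footnote i is most likely left over from the plasma radioactivity criterion, which the amendment summary records as removed.

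**Conclusion.** The concern does not call for a change. Its factual core is correct: 13 uncollected days if both late samples are given, and no extrapolation method in Section 8.3. The step from there to counting those days as zero is not supported, because the plan says the samples are taken so that excretion can be extrapolated. Recovery over the continuously collected interval is sound as defined. The study is descriptive, and 90% is a discharge threshold rather than a test of success, so no inference turns on the gap.

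The remainder is unwritten detail for a supportive figure. The radioanalysis laboratory would ordinarily show observed recovery by interval, leave the gaps visible, and label any extrapolated total as such. The size of 0.3 to 6.4 points for an affected subject rests on total radioactivity following the parent half-life and on assumed absorption and eventual recovery. A slower decline would make it larger, and the number of affected subjects cannot be known from the document. The SAP text was not available, so it may already contain a rule. Footnote i is a clerical slip.
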